8.13. Consent

As the study is purely observational, it will not affect the treatment the children receive, we propose to conduct the PERMIT observational study without seeking consent from parents/legal representatives.

This is to avoid any unnecessary burden for parents/legal guardians in approaching consent during a very sensitive time. Information about the study will be provided to all eligible patients and displayed with public areas of participating PICUs. This will explain the study to parents, family and friends and children who are able to make autonomous decisions. Parents/legal guardians may opt the child's data out of the study at any time and that the future care their child will receive will not be affected. We will also mention that no identifiable data for the PERMIT observational study will be collected.

This procedure has been acceptably used by the FEVER observational study (REC 17/NW/0026), an observational study of critically ill children's exposure and management to fever within UK PICUs, where posters and information leaflets explaining the study were available to family and friends explaining their rights to withdraw from the study at any time.

8.14. PICANET Modelling

Following the collection of PERMIT observational study data, we use the identified key patient characteristics for patients who may benefit from ERM and model the number for patients available in the UK for a future RCT by analysing the full PICANet dataset.

PICANet has ethical approval granted by the Trent Medical Research Ethics Committee (ref 05/MRE04/17) and the National Information Governance Board (NIGB) to collect personally identifiable data without consent. All PICANet data used within the PERMIT study will be anonymised prior to sharing from the local sites to the PERMIT trials office. Also, any PICANet data used to model future RCT feasibility will also be anonymised. (1)

8.15. Study procedures and assessments

8.15.1. Summary of assessments

Figure 4 Schedule of assessments for each PICU

TIMEPOINT	Study Day 1	Study Day 2-14	Study Day 15-21
ENROLMENT:			
Eligibility screening (daily)	X	X	
Enrolment to PERMIT (daily)	X	X	
ASSESSMENTS:			
Complete Unit staff and patient census (daily)		X	X
Patient-level: Clinical Status CRF. Twice daily		XX	XX
Patient-level: Observed ERM active interaction CRF (for each active interaction)		X	X
Patient-level: Summary of overnight ERM activity CRF		X	X
Ensure completion of PICANet routine data	X	X	X

Study day 1 = **First day** on the week of trial starting

Study day 2 = **Second day** on the week of trial starting

Study day 14 = **Final day** of enrolment of eligible patients

Study day 15-21 = Completion of up to 7 days of data collection for enrolled patients. No new patient enrolled during this period.

Figure 5 Schedule of assessments for individual patients

TIMEPOINT	Patient Day 2 (09:00)	Patient Day 3 (09:00-17:00)	Patient Day 4-10 (09:00-17:00)*
ENROLMENT:			
Eligibility screen	X		
Enrolment to PERMIT		X	
ASSESSMENTS:			
Patient level: Clinical Status CRF. Twice daily		XX	XX
Patient-level: Observed ERM active interaction CRF (for each active interaction)		X	X
Patient-level: Summary of overnight ERM activity CRF		X	X
Ensure complete PICANet routine data has been collected	X	X	X

Patient Day 0 = the day a patient is admitted to PICU which occurs after 09:01 and before 08:59 of the same day.

Patient Day 1 = the 1st day the patient has been in PICU at exactly 09:00. (A patient may have been admitted 10mins prior, or 23 hours prior; however, the census count is that the patient is in PICU at exactly 09:00 on the study day).

Patient Day 2 = the 2nd day the patient has been in PICU at 09:00.

Patient Day 3 = the 3rd day the patient has been in PICU at 09:00 (this is the day that ERM activities will be observed from).

Patient Day 10 is the 10th day the patient has been in PICU at 09:00 (this is the end of the 7 complete days of data collection).

*Data collection stops earlier than Day 10 if the patient is discharged from PICU/HDU care area which is managed by critical care staff who submit PICANet/PCCMDS data.

8.16. Schedule of Assessments

Figure 4 & Figure 5 summarise the schedule of assessments.

8.16.1. Clinical status

Data will be collected twice, between 09:00 and 10:00 and between 14:00 and 15:00 each day.

8.16.2. Observed ERM active interaction

CRFs will be collated hourly between 9 am and 5 pm by the local site research nurse.

8.16.3. Summary of overnight ERM activities

Daily at 09:00 researchers will retrospectively review the clinical case records to record any ERM activities that occurred overnight. Overnight is defined as the time from the end of Observed active interaction period 17:01, until 08:59 prior to the start of the next Observed active interaction period.

8.16.4. Complete PICANET routine data

Local sites will have existing PICANet routine data collection systems in place. PICANet collected admission data on all patients within 1 hour of PICU admission. PCCMDS data is collected twice a day summarising activities and interventions within each shift. Further details available in PICANet data collection manual <https://www.picanet.org.uk/data-collection/data-manuals-and-guidance/>

8.17. Adverse Event Reporting

8.17.1. Reporting Requirements

Due to the fact that there is no interventional element to the PERMIT Observational Study no additional adverse event reporting will be required. We will record any unexpected clinical events that occur during the delivery of ERM activities.

8.17.2. Source Data

In order to allow for the accurate reconstruction of the study and clinical management of the subject, source data will be accessible and maintained.

Some data may be entered directly onto the paper-based CRF prior to data entry into the REDCAP database.

The participants' medical notes generated and maintained at the site will act as source data.

8.17.3. Screening CRF Completion

Data reported on each CRF will be consistent with the source data and any discrepancies will be explained. Staff delegated to complete CRFs will be trained to adhere to:

- *Date format and partial dates*
- *Study-specific interpretation of data fields*
- *Which forms to complete and when*
- *What to do in certain scenarios, for example when a parents/guardians opt-out of data sharing from the study*
- *Missing/incomplete data*
- *Protocol and ICH-GCP non-compliances*

In all cases, it remains the responsibility of the local site's Principal Investigator to ensure that the CRF has been completed correctly and that the data are accurate. Where applicable for the study this will be evidenced by the signature of the local site's Principal Investigator

8.18. Data Handling and Record Keeping

8.18.1. Data Management

Data Management

Figure 6 PERMIT study dataflow

[figure not shown]

Figure 6 summarises PERMIT study data flow.

Participating sites will screen all eligible patients for PERMIT study. A screening log will be created at each site by the local research team and this will record local patient IDs [NHS number and own hospital Patient Identification number].

For patients that fulfil all inclusion criteria and no exclusion criteria: local research staff will record in the enrolment log 1) a unique PERMIT study ID [local site code + sequential numbered patient; provided by the Trials Office], local patient IDs [NHS number and own hospital Patient Identification number] and PICANet study ID [provided by PICANet] of all enrolled patients.

Local sites will complete CRFs for all enrolled patients using the PERMIT study ID on each record. CRFs will be paper-based initially to aid bedside data collection. At the end of each study day, paper CRFs will be collated and stored in patient-specific site files. Local sites will be responsible for the safe and secure storage of these primary documents (locked in a filing cabinet or office within the PICUs or research offices).

Local sites will input data from the paper-based CRF data onto REDCAP computer database using the PERMIT study ID for patient identification only. No identifiable patient data will be uploaded to REDCAP or shared with the PERMIT trials office.

Local sites will then access PICANet data via a customised download from the PICANet database using the PERMIT study ID. No patient identifiable data will be included in this customised download

(DoB which will be converted into age in days). The PICANet data download will be uploaded to the REDCAP database to combine with the PERMIT study CRF data.

The PERMIT study trials Office team will only access the anonymised data in the REDCAP database.

Data contained within REDCAP will be transferred securely to the University of Birmingham computer server within the PERMIT study database for statistical analysis and prognostic modelling.

8.18.2. Archiving

At the end of the study, the Chief Investigator will archive securely all centrally-held study-related documents for a minimum of ten years in accordance with ICH-GCP guidelines.

It will be the responsibility of the Principal Investigators at each site to ensure all essential study documentation and source documents (e.g. Investigator Site Files, copies of CRFs, etc.) at their sites are securely retained for at least 10 years.

Guidance on archiving will be provided in the study-specific Standard Operating Procedure (SOP). All archived documents, held centrally and locally, should be available for inspection by appropriate authorities upon request.

8.19. Site Set-up and Initiation

All participating Principal Investigators will be asked to sign the necessary agreements and supply a current CV to the PERMIT Trials Office. All members of the site research team will also be required to sign a site signature delegation log. Before commencing recruitment all sites will undergo a process of initiation and will have completed ICH-GCP training. Key members of the site research team will be required to attend either a meeting or a teleconference covering aspects of the study design, protocol procedures, collection, and reporting of data and record keeping. Sites will be provided with an electronic copy of the Investigator Site File (for local printing on-site) containing essential documentation, instructions, and other documentation required for the conduct of the study. The PERMIT Trials Office must be informed immediately of any change in the site research team.

8.20. Monitoring

8.20.1. On-site Monitoring

Monitoring will be carried out as required following a risk assessment and as documented in the monitoring plan. Any monitoring activities will be reported to the PERMIT Trials Office and any issues noted will be followed up to resolution. Additional on-site monitoring visits may be triggered, for example by poor CRF return, poor data quality, an excessive number of participant withdrawals or deviations. If a monitoring visit is required the PERMIT Trials Office will contact the site to arrange a date for the proposed visit and will provide the site with written confirmation. Investigators will allow the PERMIT study staff access to source documents as requested.

8.20.2. Central Monitoring

The PERMIT Trials Office will be in regular contact with the site research team and PICANet to check on progress and address any queries that they may have. The PERMIT Trials Office will check incoming summary of screened cases and Case Report Forms for compliance with the protocol, data consistency, missing data, and timing. Sites will be asked for missing data or clarification of inconsistencies or discrepancies. Sites will be requested to send in copies of signed Opt-out Forms and other documentation for in-house review. This will be detailed in the monitoring plan.

8.21. Audit and Inspection

The Principal Investigator will permit study-related monitoring, quality checks, audits, ethical reviews, and regulatory inspection(s) at their site, providing direct access to source data/documents. The Principal Investigator will comply with these visits and any required follow up. Sites are also requested to notify the PERMIT Trials Office of any inspections.

8.22. Notification of Serious Breaches

The sponsor is responsible for notifying the REC of any serious breach of the conditions and principles of ICH-GCP in connection with that study or the protocol relating to that study. Sites are therefore requested to notify the PERMIT Trials Office of any suspected study-related serious breach of ICH-GCP and/or the study protocol. Where the PERMIT Trials Office is investigating whether or not a serious breach has occurred sites are also requested to cooperate with the Trials Office in providing sufficient information to report the breach to the REC where required and in undertaking any corrective and/or preventive action.

Sites may be suspended from further recruitment in the event of serious and persistent non-compliance with the protocol and/or ICH-GCP, and/or poor recruitment. Any major problems identified during monitoring may be reported to the PERMIT Trial Management Group and the REC. This includes reporting serious breaches of ICH-GCP and/or the study protocol to the REC. A copy is sent to the University of Birmingham Clinical Research Compliance Team at the time of reporting to the REC.

8.23. End of Study Definition

The end of the study will be after the three-month follow-up point of the last recruited participant plus an additional 6 months of data cleaning, queries, and analysis period. The PERMIT Trials Office will notify the REC the study has ended and a summary of the clinical trial report will be provided within 12 months of the end of the study.

A copy of the end of study notification, as well as the summary report, is also sent to the University of Birmingham Research Governance Team at the time of sending these to the REC.

8.24. Statistical Considerations

8.24.1. Analysis of Outcome Measures

The prevalence and scope of ERM will be described as the proportion of patients provided with any 'active interaction' on day 3 post-admission. Cumulative prevalence for each day in PICU after day 3, up to day 10 post-admission will be calculated. Quantification of doses of ERM on each day and characteristics of patients receiving ERM will be presented using standard descriptive statistics. Further analysis will be undertaken to understand factors associated with ERM and the incidence of ERM. Multilevel multivariable logistic regression models with random effects for PICU site will be used to evaluate predictors of ERM provided on day 3. Predictors of interest will be established following PERMIT survey and expert group consensus (examples include: age, presence of PICU protocol, diagnostic category, sedation level and PIM3 probability of mortality score). To calculate incidence rates and incidence rate ratios for number of ERM interventions, accounting for variable length of PICU stay, we will use a multilevel multivariable Poisson Model.

Using the primary outcome of the prevalence of ERM, PICU and patients characteristics, we will subsequently use the UK PICANet database to identify and count potential trial population sample size using national anonymised data for all UK and Irish PICUs.

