8.6.3. Secondary outcomes

- Prevalence and incidence of ERM delivery between day 3 and day 10 post PICU admission, quantification of ERM delivered per patient, characteristics of patients receiving ERM, type of ERM interventions delivered, and factors associated with variability of delivery between PICUs.

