8.6.4. Secondary outcome assessment

- Cumulative prevalence for each day in PICU after day 3, up to day 10 post-admission with whom ERM may/may not be considered appropriate.
- Quantification of dose (duration, measured in minutes) of ERM on each day and characteristics of patients receiving ERM will be presented using standard descriptive statistics.
- Further analysis will be undertaken to understand factors associated with ERM and the incidence of ERM.
 - Multilevel multivariable logistic regression models with random effects for PICU site will be used to evaluate predictors of ERM provided on day 3. Predictors of interest will be established following the Phase 1a survey and expert group consensus (examples include: age, presence of PICU protocol, diagnostic category, sedation level and PIM3 probability of mortality score).
- To calculate incidence rates and incidence rate ratios for number of ERM interventions, accounting for variable length of PICU stay, we will use a multilevel multivariable Poisson Model.

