8.10. Data collection

To maximise efficiency and ensure we can estimate point prevalence, all study sites will recruit and collect data over the same 21 day observation period (either in November 2019 or January 2020). Patients will be recruited through the first two weeks of the PERMIT study period (e.g. study day 1 to 14) with a further week to complete follow up (study day 15-21). Individual patient data collection and observations will occur for up to 7 days after patients are eligible and recruited or until PICU discharge, whichever is sooner (e.g. data collection commenced day 3 post-admission and continued up to day 10 post-admission).

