8.10.4. PERMIT observational study patient level data

Figure 3: Screening and data collection schema for individual patients displays the daily planned data collection for individual patients.

From Day 3 of PICU admission onwards, until the patient is discharged from PICU (or day 10 of admission, whichever is sooner), patient-level data will be collected for the PERMIT study.

1) Clinical status

This will include health care interventions, ventilator requirement, sedation and coma level, presence of delirium, inotropic support and neuromuscular blocking drug usage. This data will supplement routinely collected PICANet data. Data will be collected twice, between 09:00 and 10:00 and between 14:00 and 15:00 each day.

2) Observed ERM active interaction

We will undertake a behavioural mapping procedure (44) to capture 'active interaction' versus 'no interaction' with a patient in a therapeutic rehabilitation context after local researcher training, and piloting of observation case report form. Frequency, quantity, and type of 'active interaction' of ERM delivered by physiotherapy, occupational therapy, speech & language, play, psychology, nurse and parent will be recorded.

Clinical staff performing the activity will be instructed to record planned activity and delivered activity duration in medical records. A research nurse will use this data to complete active interaction CRF.

CRFs will be collated hourly between 9 am and 5 pm by the local site research nurse. 'Active ERM interaction/interventions' will be defined using the PERMIT logic model (**Error! Reference source not found.**) and based on paediatric modification of published ICU mobility scales. (45)

With the addition of free-text for any activity performed outside of the standardized mobility scales.

This data will be recorded on the "Observed ERM active interaction" CRF.

3) Summary of overnight ERM activities

Daily at 09:00 researchers will retrospectively review the clinical case records to record any ERM activities that occurred overnight. Overnight is defined as the time from the end of Observed active interaction period 17:01, until 08:59 prior to the start of the next Observed active interaction period.

This data will be recorded on the *Summary of overnight ERM activities* CRF.

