8.11. Sample Size

We aim for a sample size of n=150 CYP. Accepting our hypothesis that there is wide variability in the current prevalence of ERM delivery across PICUs (e.g. 20%-80%: (reference: personal communication with Glasgow, Nottingham, Birmingham, Southampton PIC clinicians) we anticipate identifying any ERM use in 75/150 patients (prevalence of 50%). With 150 participants a confidence interval with a width of 8% either side of the estimate (41.7%-58.3) can be produced. This degree of accuracy is adequate for our purposes.

8.12. Future RCT Sample Size Modelling:

Using the primary outcome of the prevalence of ERM, PICU and patients characteristics, we will subsequently use the UK PICANet database to identify and count potential trial population sample size using national anonymised data for all UK and Irish PICUs. Anonymised PICANet data has been used efficiently for previous NIHR HTA funded PIC RCTs (FEVER study: HTA [15/44/01](#), *CHiP study*: HTA 05/506/03). Using PICANet admission data, on average 20,000 patients are admitted per year across 28 PICUs (averaging 2 patients/unit/day). Of these 40-45% of patients stay on PICU for ≥3 days (20% > 7 days), on average 5.5 to 6 patients/unit/week will be eligible. Enrolling patients admitted over a 14-day recruitment window in 14 units, 150 patients will be included (average n=11 patients/PICU/14 days). (1)

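### The Poisson model for ERM counts should use observed days within the day 3–10 window as its exposure and allow for variation between children in the same unit

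*Protocol*

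**What the plan says.** Protocol sections 8.6.4, 8.9.2 and 8.24.1 carry the same sentence. Its purpose is given as "To calculate incidence rates and incidence rate ratios for number of ERM interventions", and its method as "accounting for variable length of PICU stay, we will use a multilevel multivariable Poisson Model". No offset is written out, and no levels are named for this model.

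The neighbouring sentence, on the day 3 binary outcome, does name a level: "Multilevel multivariable logistic regression models with random effects for PICU site will be used to evaluate predictors of ERM provided on day 3".

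Three places define the period in which interventions are counted:
- Section 8.6.3 defines the outcome as "Prevalence and incidence of ERM delivery between day 3 and day 10 post PICU admission".
- Section 8.10.4 collects data "From Day 3 of PICU admission onwards, until the patient is discharged from PICU (or day 10 of admission, whichever is sooner").
- Section 8.10 says "Individual patient data collection and observations will occur for up to 7 days after patients are eligible and recruited or until PICU discharge", taking the earlier of the two.

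Figure 5 (section 8.15.1) schedules daytime recording on patient day 3 and on days 4 to 10. Its notes describe day 10 as the end of seven complete days.

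**The concern.** Length of PICU stay and time under observation are different quantities here. Stay includes the days before patient day 3 and any days after day 10, when no ERM is recorded. A day 3–10 count divided by total stay is not a daily rate. Its error depends on stay, which is likely to move with predictors such as diagnosis, sedation and severity.

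The second issue is the distribution. A Poisson count per child with a unit effect assumes that, after covariates, children in the same unit differ only by chance around a common rate. Section 8.10.4 pools interactions by physiotherapy, occupational therapy, speech and language, play, psychology, nursing and parents. Extra variation between children is therefore likely, and standard errors for child-level predictors would then be too small.

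At stake is the list of factors reported as associated with ERM. Patient characteristics identified in this study also feed the modelling of a future trial population (sections 8.14 and 8.24.1).

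**Working it through.** **The protocol's own figure.** None is stated for the count model. The nearest is the interval of 41.7% to 58.3% for 75/150 in section 8.11. The exact (Clopper–Pearson) interval is 41.74% to 58.26%, so that figure is reproduced. It concerns the primary prevalence and does not depend on the count model.

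**1. Exposure, if total stay is used.** Let L be the last patient day in PICU, counted as in Figure 5. With days 3 to 10 counted inclusively, observed days are min(L, 10) − 2. The apparent daily rate is the true rate × (min(L, 10) − 2)/L. The true rate of 2 per day is illustrative.

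| L | Observed days | Observed/total | Apparent rate at a true 2 per day |
|---|---|---|---|
| 4 | 2 | 0.50 | 1.0 |
| 10 | 8 | 0.80 | 1.6 |
| 30 | 8 | 0.27 | 0.53 |

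If the window is capped at seven days, the ratio is 0.70 at L = 10 and 0.23 at L = 30. The factor rises and then falls with stay, so a linear covariate for stay would not correct it.

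Long stays are common. Section 8.12 says "Of these 40-45% of patients stay on PICU for ≥3 days (20% > 7 days"), so 20/45 = 44% to 20/40 = 50% of eligible children stay more than 7 days. Fitting an assumed exponential tail to 20%/42.5% puts about 30% beyond day 10 and gives an overall rate of about 0.55 of the true one. Under the same tail:
- a null predictor correlated 0.2 to 0.4 with stay gets a rate ratio of 0.98 to 0.95 per SD, a small shift;
- with no extra-Poisson variation, the total-stay offset alone raises the type I error of a null child-level predictor to 0.18–0.38, at assumed rates of 0.7 to 3 per day;
- the in-window offset gives 0.044–0.057.

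**2. Dispersion, with the correct exposure.** If the variance is φ times the mean and the model assumes φ = 1, the test statistic is too large by √φ. The type I error is then 2 × (1 − Φ(1.96/√φ)).

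| φ (assumed) | Type I error at nominal 5% |
|---|---|
| 1 | 0.05 |
| 1.5 | 0.11 |
| 2 | 0.17 |
| 4 | 0.33 |

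For a gamma-distributed child effect, φ = 1 + CV² × mean count. At an assumed 0.7 interventions per day over about 5 observed days, the mean is 0.7 × 5 = 3.5. A between-child CV of 0.5 then gives φ = 1 + 0.25 × 3.5 ≈ 1.9.

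**3. Simulation checks** (assumed inputs, null predictor):
- 150 children in 14 sites, 0.7 to 3 interventions per day, child variance 0.25 to 1.0, fixed site effects: Poisson type I error 0.22–0.72. Adding only a common dispersion scale lowers it to 0.09–0.16.
- 14 units × 11 children, 0.5 to 1.5 per day, CV 0.5 to 1.0: Poisson 0.14–0.55, negative binomial 0.06–0.08.
- Site-level predictor, with a site random effect: 0.097, 0.102 and 0.112 at child variance 0, 0.5 and 1.0. Child variance makes little difference; the excess over 0.05 comes from having only 14 sites.

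**The case against.** A reader might infer that the planned rates are distorted and the p-values far too small. The protocol does not support that as a flat statement, for four reasons.

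- **Exposure.** It never says that total stay is the offset. Section 8.6.3 confines the outcome to days 3 to 10, and collection stops at discharge if that is sooner. Within that window, time at risk varies because children leave at different times, so accounting for variable stay may mean exactly that. This stands, and it makes the exposure problem conditional on the literal reading. It does not remove the problem: three sections name stay, and none names observed days.
- **Levels.** The site random effect is stated for the logistic model only. The word multilevel does not exclude a child-level term in the count model, and one of the remedies below is itself a multilevel Poisson model. This also stands.
- **Size.** Strong variation between children is not in the protocol. Its only variability figure is the 20%–80% range across PICUs in section 8.11, which a unit effect addresses. The error rates therefore rest on assumed dispersion, and they apply to child-level predictors.
- **Role.** The analysis is secondary and exploratory, with no test or alpha set. Offsets and overdispersion checks are often left to a statistical analysis plan. That would answer a silent protocol, but this one names both the distribution and the quantity to be adjusted for, and that quantity does not match the data collection.

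Section 13.8 reports that the observational study has already been carried out. This limits the value of rewording the protocol, but the correction needs no new data.

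**Conclusion.** The point holds in a limited form. The named exposure, read literally, does not match the observation window. Rates would then be understated by a factor that depends on stay (0.50, 0.80 and 0.27 at 4, 10 and 30 days). If in-window days are meant, this problem disappears, but the text must say so.

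A Poisson count per child with only a unit effect also leaves variation between children unmodelled. If that variation exists, as is likely, standard errors for age, diagnosis, sedation and PIM3 are too small. The nominal 5% error becomes about 11% at dispersion 1.5, 17% at 2 and 33% at 4, and stays at 5% if there is no extra variation. These dispersion values, the daily rates and the stay tail are assumptions.

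Site-level predictors, such as presence of a PICU protocol, are hardly affected. The primary prevalence outcome and the precision claimed for n=150 are unaffected. The change is worth making because it is concrete and nearly free.

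**What to change.** In sections 8.6.4, 8.9.2 and 8.24.1:

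1. Replace the reference to length of PICU stay with an offset of log(observed PICU days from patient day 3 to the earlier of discharge or day 10).
2. Reconcile the seven days in section 8.10 and the Figure 5 notes with the eight dates from day 3 to day 10, so that the offset counts the days on which interventions could be recorded.
3. Fit a multilevel negative binomial model with a PICU random effect, or a Poisson model with child-level as well as PICU-level random effects. A common dispersion scale alone is a weaker repair, since it left type I error at 0.09–0.16 in the check above.

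The cost is a change of analysis wording and somewhat wider intervals. No additional data are needed.
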